## **2. LIST OF ABBREVIATIONS**

Include a list of all abbreviations used in the TSAP

Term	Definition / description
AE	Adverse event
BRPM	Blinded report planning meeting
CR	Complete response
CTCAE	Common Terminology Criteria for Adverse Events
CTP	Clinical trial protocol
CTR	Clinical trial report
ECOG	Eastern Cooperative Oncology Group
eCRF	Electronic case report form
EGFR	Epidermal growth factor receptors
EOT	End of Treatment
ICH	International Conference on Harmonisation
iPD	Important protocol deviation
MedDRA	Medical Dictionary for Regulatory Activities
MQRM	Medical Quality Review Meeting
NSCLC	Non-small cell lung cancer

Term	Definition / description
PT	Preferred term
Q1	Lower quartile
Q3	Upper quartile
REP	Residual effect period
SAE	Serious adverse event
SD	Stable disease
SOC	System organ class
StD	Standard deviation
TSAP	Trial statistical analysis plan

### **3. INTRODUCTION**

As per ICH E9 ([1](#)), the purpose of this document is to provide a more technical and detailed elaboration of the principal features of the analysis described in the protocol, and to include detailed procedures for executing the statistical analysis of the primary and secondary variables and other data.

This TSAP assumes familiarity with the Clinical Trial Protocol (CTP), including Protocol Amendments. In particular, the TSAP is based on the planned analysis specification as written in CTP Section 7 “Statistical Methods and Determination of Sample Size”. Therefore, TSAP readers may consult the CTP for more background information on the study, e.g., on study objectives, study design and population, treatments, definition of measurements and variables, planning of sample size, randomization.

SAS® Version 9.4 or later will be used for all analyses.

#### **4. CHANGES IN THE PLANNED ANALYSIS OF THE STUDY**

The following changes have been made in the planned analyses prior to database lock:

- The trial protocol was amended on 15Feb2018 (global amendment 2) to document early study termination due to slow enrollment. The number of patients randomized in this trial is expected to be approximately 25 patients instead of 50.
- Per current standard operating procedures, important protocol violations will be summarized as important protocol deviations.

## **5. ENDPOINT(S)**

### **5.1 PRIMARY ENDPOINT(S)**

The primary endpoint of this study is the occurrence of adverse events (AEs) leading to dose reduction of Afatinib.

This endpoint is a safety endpoint; therefore, analyses are described in [Section 7.8](#).

### **5.2 SECONDARY ENDPOINTS**

#### **5.2.1 Key secondary endpoints**

This section is not applicable as no key secondary endpoints have been specified in the protocol.

#### **5.2.2 (Other) Secondary endpoints**

The secondary endpoints of the study are

- Occurrences of CTCAE grade  $\geq 3$  diarrhea,
- Occurrences of CTCAE grade  $\geq 3$  rash/acne+,
- Occurrences of CTCAE grade  $\geq 3$  stomatitis+,
- Occurrences of CTCAE grade  $\geq 3$  paronychia+,
- Time to first dose reduction of Afatinib caused by AEs.

Refer to CTP Section 5.2.1 and [Section 7.8](#) of this TSAP for more details. The terms flagged by a “+” represent MedDRA preferred terms reported together as one grouped term for analysis.

## 6. GENERAL ANALYSIS DEFINITIONS

### 6.1 TREATMENTS

For basic study information on treatments administered, assignment of dose group and selection of doses, see CTP Section 4. All eligible patients will be assigned to receive Afatinib 30 mg QD in this study. The dose may be reduced to 20 mg QD during the study as described in Section 4.4 of the CTP. Unless otherwise stated, treated patients will be presented under the starting dose, i.e. 30 mg Afatinib.

[Table 6.1:1](#) displays the study periods defined for 1200.209. In this study, treatment is administered in courses of 28 days. The follow-up period extends from the date of last administration of study treatment to the follow-up visit, which should occur 28 to 35 days after the last administration of study treatment. After completion of the follow-up period, vital status will be monitored every 3 months until the end of the trial, which is defined as approximately 12 months after the last patient enters the study.

**Table 6.1: 1 Study periods**

Study Period	Start time	Stop time
Screening	Date of informed consent	Date of 1 st administration of study treatment – 1 day
On-treatment	Date of 1 st administration of study treatment	Date of last administration of study treatment
Residual effect period	Date of last administration of study treatment + 1 day	Date of last administration of study treatment + 28 days
Follow-up period (includes residual effect period)	Date of last administration of study treatment + 1 day	Date of follow-up visit (28-35 days after date of last administration of study treatment).
Post-study vital status	Date of follow-up visit +1	End of trial

### 6.2 IMPORTANT PROTOCOL DEVIATIONS

The following table ([Table 6.2: 1](#)) defines the different categories of important protocol deviations (iPD) to be documented during the study. No per-protocol analyses will be performed for this study; however, patients identified with some iPDs may be excluded from certain analyses as specified in the table. Protocol deviations will be reviewed periodically at MQRMs and BRPMs prior to database lock.

Table 6.2: 1 Important protocol deviations

Category / Code	Description	Example/Comment	Excluded from	Automatic /Manual
A	Entrance criteria not met			
	A1	Inclusion criteria not met		
	A1.1	Disease criteria not met	Inclusion criteria 1 or 2 not met as specified in the protocol per IE CRF.	None Automatic
	A1.2	ECOG not 0 or 1.	Inclusion criteria 4 not met or ECOG recorded on screening physical exam CRF not 0 or 1.	None Automatic
	A1.3	Age at enrollment not $\geq$ 70 years	Inclusion criterion 3 not met or AGE<70 years on demographics CRF.	None Automatic
	A1.4	Failure to recover from previous therapy-related toxicity	Inclusion criterion 6 not met.	None Automatic
	A1.5	Laboratory values do not meet inclusion criteria	Inclusion criterion 5 not met.	None Automatic
	A1.6	Other inclusion criteria not met	Inclusion criteria 7 or 8 not met.	IN7 =None; IN8 = see B1 below Automatic
	A2	Exclusion criteria not met		
	A2.1	Prior therapy not consistent with exclusion criteria	Exclusion criteria 1, 2, 3, 4, or 5 not met.	None Automatic
	A2.2	Patient has excluded medical condition	Exclusion criteria 7, 8, 9, 10, 11, 12, 13, 14, or 15 not met.	None Automatic
	A2.3	Other exclusion criteria not met	Exclusion criteria 6, 16 or 17.	None Automatic
B		Informed consent		
	B1	Informed consent not available/not	Informed consent date missing; no signature on ICF	All Automatic /Manual

Category / Code	Description	Example/Comment	Excluded from	Automatic /Manual
	done			
B2	Informed consent given late	Informed consent date <actual consent date> after Visit 1 date <Visit 1 date>	None	Automatic /Manual
C	Trial medication			
C1	Incorrect trial medication taken	Review of dose(s) recorded on the drug administration and dose change CRFs against IWRS reports at MQRM/RPM.	None	Manual
C2	Dose reduction or treatment discontinuation not according to protocol.	Review of reported dose changes and AEs at MQRM/RPM for compliance with Sections 3.3.4 and 4.4.1 of the CTP.	None	Automatic /Manual
C3	Non-compliance with trial medication.	Afatinib doses missed for reasons other than drug-related AEs is >25% of the dispensed doses as indicated on compliance CRF.	None	Automatic /Manual
D	Concomitant medication			
D1	Use of prohibited concomitant medication.	Review of concomitant medication listings at MQRM/RPM for prohibited medications as defined in Section 4.2.2 of the CTP.	None	Manual

Note: Missing visits, evaluations, and tests will be considered missing data, not protocol deviations.

### 6.3 PATIENT SETS ANALYSED

The following sets of patient data will be used for analyses:

- Enrolled set:  
This patient set includes all enrolled (screened) patients who signed informed consent, whether treated or not.
- Treated set (TS):  
This patient set includes all patients who were dispensed study medication and were documented to have taken at least one dose of study treatment. All planned efficacy and safety analyses will be based on the TS.

## **6.5 POOLING OF CENTRES**

Descriptive summaries will present data from all centers combined. Center/country will not be included in any statistical models.

## **6.6 HANDLING OF MISSING DATA AND OUTLIERS**

Missing or incomplete AE dates will be imputed according to BI standards (see ‘Handling of missing and incomplete AE dates’). (4) A separate category for missing values will be displayed in frequency tables only if there are missing values for the variable being summarized.

Time since diagnosis of NSCLC will be calculated from the date of diagnosis and the date of screening. If a partial date of diagnosis is provided, the following imputation rules will be used:

- If the day is missing but month and year are present, impute day as the first day of the month.
- If only the year of diagnosis is present, impute month and day of diagnosis to January 1.

For partial treatment discontinuation dates, the following logic will apply:

- If the patient died within the same month and year as treatment discontinuation, use the date of death as the treatment discontinuation date.

- Otherwise, if day is missing, but month and year are present, use the last day of the month.

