- d FU: all patients should have a follow-up (FU) visit 28+7 days after the permanent discontinuation of afatinib
- e Written informed consent must be obtained before any protocol specific screening assessment is performed
- f A 12-lead resting digital electrocardiogram (ECG) will be performed at Screening and reviewed by the investigator. Refer to [Section 5.2.4](#) for details
- g Physical exam: includes a thorough cardiopulmonary, abdominal and regional lymph node exam and an assessment of the mental and neurological status. No need to repeat the physical exam on C1V1D1 if within three calendar days of the screening physical exam and the patient is deemed stable by the investigator
- h Vital signs: includes respiratory rate, pulse, temperature and blood pressure
- i Safety lab: CBC: include white blood cell count, neutrophil and bands, differential, hemoglobin, hematocrit and platelet count. Serum chemistries: include sodium, potassium, chloride, bicarbonate, BUN, creatinine, glucose, AST, ALT, GGT, total bilirubin, alkaline phosphatase, calcium, magnesium. See [Section 5.2.3](#)
- j Additional laboratory assessments should be performed if clinically indicated
- k Urine analysis: include pH, protein, glucose, ketones, blood, leucocytes, nitrite, bilirubin, urobilinogen, and specific gravity. In case of pathological finding, further evaluation should be performed and results documented in the source document
- m Interactive Response Technologies (IRT): patient's screening, all drug dispensation visits and EOT will be collected in the IRT system
- n Adverse event: from 28 days after last trial drug administration new AEs will only be collected, documented and reported if they are considered related to trial drug
- o Concomitant therapy: during FU concomitant therapy only needs to be recorded if indicated for the treatment of an AE

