#### 6.2.3 End of treatment visit

End of treatment visit should be performed within 7 calendar days after permanent discontinuation of treatment, regardless of the reason. If the decision to discontinue study treatment is taken during a scheduled visit, the EOT visit should be performed instead of the scheduled visit.

Proprietary confidential information.

© 2018 Boehringer Ingelheim International GmbH or one or more of its affiliated companies. All rights reserved.

This document may not - in full or in part - be passed on, reproduced, published or otherwise used without prior written permission.

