#### **6.2.4 Follow-up visit**

The follow-up (FU) visit is performed 28-35 days after the last dose of afatinib and is primarily to collect follow-up safety information.

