For patients with AEs leading to dose reduction:

Time to first dose reduction [days] = (date of first dose reduction) – (date of first administration of study treatment) + 1

For patients without AEs leading to dose reduction:

Time to first dose reduction (censored) [days] = (date of last administration of study treatment) – (date of first administration of study treatment) + 1

The Kaplan-Meier estimate of median time to first dose reduction of study treatment due to AE will be presented, if calculable. In addition, the cumulative percentage of patients with dose reductions due to each AE by time interval will be summarized..

*Secondary endpoint: Occurrence of CTCAE grade 3 or higher diarrhea, rash/acne+, stomatitis+ and paronychia+*

The frequency and percentage of treated patients reporting project-defined grouped terms, including diarrhea, rash/acne+, stomatitis+ or paronychia+, will be summarized. The frequency of events will be summarized by highest CTC grade, i.e. grade 3, 4 or 5, treatment, SOC and PT.

Events designated with a ‘+’ are project-defined grouped terms. Definitions of the project-defined groupings are included in the technical TSAP. In the summary table, the grouped AEs will replace the MedDRA PTs for all AEs included in the grouped term. A reference table presenting the grouped terms and the MedDRA PTs within each grouping will also be produced.

Listings for events within the grouped terms of diarrhea, rash/acne+, stomatitis+ or paronychia+ will display intensity, time to onset and clinical consequences of these events.

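### SAP 6.6 completes a partial discontinuation date to month end or death without capping it at the EOT visit, so exposure and censoring time can be overstated by up to 27 to 30 days in an affected patient (minor)

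*SAP*

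**What the plan says.** SAP 6.6 has two rules for a treatment discontinuation date that lacks the day. If the patient died in that month and year, "use the date of death as the treatment discontinuation date". For everyone else: "Otherwise, if day is missing, but month and year are present, use the last day of the month". The internal standard cited in the same section is for AE dates. Nothing else in the available text bounds the imputed date.

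The protocol provides a bound. Its section 6.2.3 reads: "End of treatment visit should be performed within 7 calendar days after permanent discontinuation of treatment, regardless of the reason". The flow chart times the same visit within 7 days of the last treatment.

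Three derivations run from the last-dose date:
- exposure time (SAP 7.7);
- the censoring time for time to first dose reduction (SAP 7.8.1);
- the end of the on-treatment AE window (SAP 7.8.1), which matches the stop of the residual effect period in SAP Table 6.1:1, "Date of last administration of study treatment + 28 days".

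The SAP does not say that the discontinuation date imputed in 6.6 supplies this last-dose date. The protocol treats the two as the same day. For the follow-up (FU) visit, flow chart note d says "all patients should have a follow-up (FU) visit 28+7 days after the permanent discontinuation of afatinib", while section 6.2.4 has it "performed 28-35 days after the last dose of afatinib".

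**The concern.** Apart from a death in the same month, the rule picks the latest date the month allows. A patient seen at an EOT visit has already stopped by that day, so an imputed last dose after the visit contradicts a date already in the database. The SAP uses one known upper bound, death, and leaves out the one that every patient is meant to have.

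The error is never negative. It lengthens exposure. It also keeps a patient who is off drug, and can no longer have a dose reduction, in the Kaplan-Meier risk set. That pushes the estimated reduction-free time upward for a named secondary endpoint. In the extreme it produces a follow-up period that ends before it starts.

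**Working it through.** The documents give no figure for imputation error, so there is none to reproduce. The only design figure, the 19.2% half-width in Protocol 7.6, is not an input here. It does reproduce: 1.96 × √(0.6 × 0.4 / 25) = 0.192.

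**Inputs.** Month length L = 28 to 31 days. True last dose on day d of the month. EOT delay k = 0 to 7 days (Protocol 6.2.3). FU visit 28 to 35 days after the last dose (Protocol 6.2.4). About 25 patients (Protocol 3.1).

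**1. Largest error under the month-end rule.** The error is L − d, largest at d = 1: 27, 28, 29 or 30 days for L = 28, 29, 30 or 31. The date-of-death rule has the same maximum if death is on the last day of the month.

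**2. Largest error with an EOT cap.** The error is min(L, d + k) − d, which cannot exceed k, so at most 7 days if EOT is on time.

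**3. Example.** First dose 1 January 2018, true last dose 1 March 2018 with the day missing, EOT visit on 8 March.

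| Last dose taken as | Exposure or censoring time | AE window ends |
|---|---|---|
| True date, 1 March | 60 days | 29 March |
| SAP rule, 31 March | 90 days | 28 April |
| EOT cap, 8 March | 67 days | 5 April |

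Under the SAP rule the AE window closes 30 + 28 = 58 days after the true last dose.

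**4. Typical size in living patients.** Take d and k as uniform, which is an assumption. The imputed date falls after EOT when L > d + k. For L = 31 that is (8 × 30 − 28) / (8 × 31) = 212/248 = 85.5% of combinations. For L = 28 it is 188/224 = 83.9%. For L = 31 the mean error is 15.0 days under the SAP rule and 784/248 ≈ 3.2 days with the cap.

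**5. Impossible follow-up period.** The imputed last dose falls after the earliest FU visit when L > d + 28: d = 1 in a 30-day month, d = 1 or 2 in a 31-day month. In the example, an FU visit on 29 March would precede an imputed last dose on 31 March.

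**6. Effect on summaries.** One affected patient moves mean exposure by at most 30/25 = 1.2 days, or by 15/25 = 0.6 days at the mean error in step 4.

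**7. Effect on AE counts.** Flow chart note n limits collection of new AEs from day 28 after the last dose to those considered related. Protocol Table 5.2.2.2:1 narrows this to related serious AEs after the FU visit. Where the patient died in the same month, live time beyond the true 28-day window is at most 31 − (1 + 28) = 2 days.

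**The case against.** Four objections have force.

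- **The link is inferred.** The rule names a discontinuation date; the derivations name the last administration. Parts of both documents are not visible, so the rule may serve other analyses. This stands, and the finding is therefore conditional. The protocol's interchangeable use of the terms makes the link likely, and the SAP should state it.
- **The EOT date may be absent when it is needed.** A site that held the EOT visit is well placed to record the full stop date. A missing day is most plausible after an early death or loss to follow-up, when there may be no EOT visit. This also stands: the cap helps only where the visit took place.
- **Any imputation is approximate, and a late date favours capturing AEs.** That is fair for AEs. It does not justify a date later than a visit at which treatment had already ended, and it works the wrong way for censoring.
- **The results hardly move.** All analyses are descriptive. The Kaplan-Meier steps change only if another patient's dose reduction falls within the extra days.

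Two stronger readings are tempting. A reader might infer from the 58-day window that off-drug AEs would be counted freely for an extra month. Step 7 shows otherwise: only related new events could be reclassified in any number. A reader might also infer that the primary result is biased. A dose reduction has to precede the last dose, so moving the last-dose date later leaves that proportion essentially unchanged.

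**Conclusion.** The point holds as a minor one. The stated rule has no cap at the EOT visit and can place the last dose after that visit. The worst case is 27 to 30 days too long for exposure and for the censoring time of time to first dose reduction, always in that direction. The AE window end shifts by the same amount, with little effect on AE counts.

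This rests on three conditions: the imputed date is used as the last-dose date; the day is missing; and an EOT visit was held. The documents do not say how many dates will be partial; few are likely. The 15.0-day and 3.2-day means, and the 84% to 86% of imputed dates falling after EOT, depend on the uniform assumption. The maxima under the SAP rule do not, and the 7-day maximum with the cap needs only an EOT visit held on time.

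**What to change.** Replace both bullets in SAP 6.6 with one rule:

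> Impute the earliest of the last day of the month, the date of death and the EOT visit date (if held), but never earlier than the last documented dose. The resulting date is used as the date of last administration.

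With EOT inside its 7-day window, the largest overstatement falls from 30 to 7 days.

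Where no EOT visit took place, the FU date minus 28 days may look like a natural substitute. It should not be used: an early FU visit would put the imputed date before the true last dose.

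The cost is a short SAP edit and slightly more derivation code, since several date sources and a floor are involved. No new data are needed. There is no gain for patients without an EOT visit.

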## **6.7 BASELINE, TIME WINDOWS AND CALCULATED VISITS**

In general, baseline values are the last non-missing measurements collected prior to the first administration of study treatment. Typically, this is the value collected at the screening visit.

Nominal visit numbers as recorded in the eCRF will be used; there will be no windowing of visits. Study day will be calculated relative to the date of first administration of study treatment. The day prior to date of first administration will be 'Day -1', and the date of first administration of study treatment will be 'Day 1'. There will be no 'Day 0'.

## **7. PLANNED ANALYSIS**

Unless otherwise specified, summary statistics for continuous data will include: N, mean, StD, minimum, median and maximum

Tabulations of categorical data will include all possible categories and will display the number of observations in each category with the percentage (%) of the respective treatment group, unless otherwise specified. Percentages will be rounded to one decimal place. A category for missing values will be displayed only if there are actual missing values for a variable.

### **7.1 DEMOGRAPHIC AND OTHER BASELINE CHARACTERISTICS**

Only descriptive statistics are planned for this section of the report. Demographic and baseline characteristics to be summarized include:

- Age [years]
- Sex (male/female)
- Race and ethnicity (as defined in the eCRF)
- Smoking and alcohol use status (as defined in the eCRF)
- Height [cm], weight [kg] and body mass index [kg/m^2]
- ECOG performance status
- EGFR mutation status (negative, L858R, Del19, both, other)
- Oncology history
- Medical conditions,
- Concomitant medications.
- Treatment exposure and compliance
- Vital signs

### **7.2 CONCOMITANT DISEASES AND MEDICATION**

Only descriptive statistics are planned for this section of the report.

### **7.3 TREATMENT COMPLIANCE**

Treatment compliance during each visit interval will be calculated as:

$$\text{Treatment compliance (\%)} = \frac{\text{Number of doses taken} \times 100}{\text{Number of doses that should have been taken}}$$

Overall treatment compliance is the weighted average of available treatment compliance for each visit interval weighted by number of days within the interval. For example: patient whose compliance score=80% at Visit 3, 100% at Visit 4, 100% at Visit 5, the overall compliance for this patient is [(compliance score date at V3 – treatment start date at V2)\*0.8 + (compliance score date at V4 - treatment start date at V3)\*1 + (compliance score date at V5 - treatment start date at V4)\*1]/( compliance score date at V5 - treatment start date).

Overall compliance will be summarized descriptively, and the number and percentage of treated patients reported as compliant with study treatment, defined as overall compliance > 75%, and non-compliance, defined as overall compliance ≤75%, will be summarized.

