#### **4.3 TREATMENT COMPLIANCE**

The study medication will be given in accordance with the protocol and the instructions of a site investigator.

The appropriate number of afatinib tablets for 28 days of treatment will be provided to patients to be self-administered at home.

Patients will be asked to bring the remaining trial medication to the investigator site for a compliance check according to the [Flowchart](#). The remaining film-coated tablets will be counted by the investigator/site staff and recorded at the investigator site. Discrepancies between the number of tablets remaining and the calculated number of tablets the patients should have taken must be documented and explained. At the end of each 28 day period, any remaining medication will be collected. If the patient is eligible for further treatment, a new bottle of study medication must be dispensed.

Patient's repeatedly missing scheduled on-treatment study visits, unless due to exceptional circumstances, should be discussed with the BI trial monitor and be evaluated for compliance. A maximum of 25% of the dispensed afatinib doses may be missed for other reasons than drug-related AEs. Patients who miss afatinib treatment more frequently are considered non-compliant.

The investigator and/or the sponsor can withdraw a patient from the study in the event of serious and persistent non-compliance which jeopardizes the patient's safety or render study results for this patient unacceptable.

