#### **4.4 MANAGEMENT OF DOSE REDUCTION AND EXPECTED ADVERSE EVENTS**

##### **4.4.1 Management of dose reduction for afatinib**

Afatinib treatment related toxicities will be managed by treatment interruptions and subsequent dose reductions according to the schedule described in [Table 4.4.1: 1](#). Dose reductions will apply to individual patients only. Once the dose has been reduced, it cannot be increased later.

Proprietary confidential information.

© 2018 Boehringer Ingelheim International GmbH or one or more of its affiliated companies. All rights reserved.

This document may not - in full or in part - be passed on, reproduced, published or otherwise used without prior written permission.

To prevent the development of more severe adverse events, treatment related diarrhoea, dermatologic adverse events or mucositis/stomatitis should be managed early and proactively as described in [Section 4.4.2](#).

Table 4.4.1: 1 Dose reduction scheme for afatinib

CTCAE a Adverse Events related to afatinib	Action	Dose reduction scheme
Grade 1 or Grade 2	No interruption b	No dose adjustment
Grade 2 (prolonged c or intolerable) or Grade 2 renal dysfunction or Grade $\geq 3$	Interrupt until Grade $\leq 1$ b	Resume treatment with dose reduction by 10mg decrements d

a NCI Common Terminology Criteria for Adverse Events V 4.0 ([R12-2532](#))

b In case of diarrhoea, anti-diarrhoeal medicinal products (e.g. loperamide) should be taken immediately and continued for persistent diarrhoea until loose bowel movements ease.

c  $\geq 48$  hours of diarrhoea and/or  $\geq 7$  days of rash

d If patient cannot tolerate 20mg/ day, afatinib should be permanently discontinued

Interstitial Lung Disease (ILD) should be considered if a patient develops acute or worsening of respiratory symptoms in which case treatment should be interrupted pending evaluation. If ILD is diagnosed, afatinib should be discontinued and appropriate treatment initiated as necessary.

In the event of any unrelated adverse events, the investigator may choose to interrupt the medication for up to 14 days, but no dose reduction should occur. If the medication is interrupted for more than 14 days for any reason, the decision to continue with afatinib will be made by the BI clinical monitor in agreement with the investigator.

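### SAP 7.3 weights interval compliance by calendar days; if hold days are not doses due, a patient near the 75% limit can be misclassified in either direction

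*SAP*

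**What the plan says.** SAP 7.3 works in three steps.

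- **Interval score.** "Treatment compliance during each visit interval will be calculated as" doses taken times 100, divided by the doses due in that interval.
- **Overall score.** "Overall treatment compliance is the weighted average of available treatment compliance for each visit interval weighted by number of days within the interval". The illustration, a "patient whose compliance score=80% at Visit 3, 100% at Visit 4, 100% at Visit 5", uses date differences as weights. It gives neither interval lengths nor a numerical result.
- **Classification.** Patients are counted as compliant or not, "defined as overall compliance > 75%, and non-compliance, defined as overall compliance ≤75%, will be summarized".

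The SAP does not say whether days on a treatment hold count as doses due. The only related rule is in SAP 7.7, which keeps off-treatment time in the exposure calculation.

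Protocol 4.4.1 makes holds a planned part of treatment: "Afatinib treatment related toxicities will be managed by treatment interruptions and subsequent dose reductions". Protocol 4.1.4 sets one dose per day.

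Two other places use a 25% limit, and both count doses. Protocol 4.3 says: "A maximum of 25% of the dispensed afatinib doses may be missed for other reasons than drug-related AEs". Deviation code C3 in SAP 6.2 reads: "Afatinib doses missed for reasons other than drug-related AEs is >25% of the dispensed doses as indicated on compliance CRF".

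**The concern.** An average of ratios is guaranteed to return the overall ratio only if each ratio is weighted in proportion to its own denominator. Here the denominator is doses due, but the weight is days. The two are proportional when no treatment is held. In an interval with a hold they are not: a score based on the few remaining doses carries the weight of the whole interval.

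The patients exposed to this are those with a hold whose adherence differs between intervals. Under Table 4.4.1:1 a hold precedes each reduction made for a drug-related AE, and Protocol 7.6 plans around a 60% AE-led reduction rate taken from an earlier trial. Holds should therefore be common. At stake are the reported mean compliance and the counts on either side of 75%.

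**Working it through.** **Inputs**

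- Interval score, day weights and the 75% cut: SAP 7.3.
- One dose per day: Protocol 4.1.4. Courses of 28 days: Flow Chart, footnote b.
- Hold length: 14 days, for illustration. Protocol 4.4.1 uses 14 days as the limit for interruptions due to unrelated AEs and as the point beyond which continuing needs joint agreement.
- Assumption: hold days are not doses due. The alternative is tested in step 4.

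**Formulas**, with d = days, u = doses due and t = doses taken in each interval:

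- By days (SAP 7.3): Σ(d × t/u) / Σd
- By doses: Σt / Σu

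The two agree when d is proportional to u, and also when every interval has the same score.

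**Step 1. The SAP's illustration.** There is no stated result to reproduce. With no hold, both formulas agree whatever the interval lengths. On assumed lengths of 7, 7 and 14 days the result is (7 × 0.8 + 7 + 14)/28 = 95.0%. On three 28-day intervals it is (0.8 + 1 + 1)/3 = 93.3%.

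**Step 2. Two 28-day intervals, 14-day hold in the first (14 then 28 doses due).**

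| Doses taken | By days | By doses |
|---|---|---|
| 7/14, then 25/28 | (28 × 0.5 + 25)/56 = 39/56 = 69.6%, non-compliant | 32/42 = 76.2%, compliant |
| 14/14, then 17/28 | (28 × 1 + 17)/56 = 45/56 = 80.4%, compliant | 31/42 = 73.8%, non-compliant |

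Each dose due in the held interval counts double (28 days of weight for 14 doses), so the error goes both ways.

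Over all possible dose counts in this layout, the two results differ by up to 16.7 points. Of 435 combinations, 22 change class: 16 become non-compliant under the SAP rule and 6 become compliant. With a 7-day hold the largest difference is 7.1 points, and 13 of 638 combinations change class. These are counts of combinations, not probabilities.

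**Step 3. The early Flow Chart schedule.** Compliance checks up to Course 2 Day 15 give intervals of 7, 7, 14 and 14 days. With a 10-day hold in the third and doses of 7/7, 7/7, 1/4 and 11/14:

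- by days: (7 + 7 + 14 × 0.25 + 11)/42 = 28.5/42 = 67.9%;
- by doses: 26/32 = 81.25%.

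**Step 4. The other reading: hold days are doses due.** The first patient in step 2 becomes 7/28 then 25/28. Both formulas give 32/56 = 57.1%. The weighting problem disappears, but the hold itself now lowers compliance.

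**Step 5. The date arithmetic in the illustration.** Each numerator weight runs from a treatment start date at the earlier visit, while the denominator is the whole calendar span. If that start date is the restart after a hold, the weights do not add up to the denominator. A patient who took every due dose over 56 days, with a 14-day hold between a visit and the restart, scores (28 + 14)/56 = 75.0% and is classed non-compliant.

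**Step 6. Longer treatment.** With one 14-day hold in two 28-day intervals, patients whose dose-based value lies between about 69.0% and 83.3% can change class. With one such hold in twelve intervals, the range narrows to about 74.2% to 78.3%.

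**The case against.** The strongest reply is that the problem depends on a reading the SAP does not state. If hold days count as doses due, day weighting and dose weighting agree, and the real gap is an undefined denominator. This stands: pooling the doses without defining doses due would leave two programmers free to get different answers, so both changes are needed.

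The second reply is that nothing rests on the result. This also stands. SAP 7.3 summarises compliance descriptively, SAP 6.2 plans no per-protocol analysis, and code C3 excludes no one. A reader might infer that the trial's tolerability findings are distorted, because holds fall on the patients with toxicity. The documents do not support that. The primary endpoint is AEs leading to dose reduction, the secondary endpoints are grade 3 or higher events and time to first reduction, and none of them uses compliance.

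A reader might also infer that the pooled ratio restores the protocol's 25% rule. It does not. Protocol 4.3 and C3 use dispensed doses and leave out doses missed for drug-related AEs, and C3 is assessed separately from the compliance CRF. Pooling corrects the weights in SAP 7.3 and does nothing else.

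Finally, the examples are chosen to lie near the limit. That is fair: they show that misclassification is possible in both directions, not how often it occurs.

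**Conclusion.** The point holds as a minor one. If hold days are not doses due, SAP 7.3 over-weights any interval with a hold, and a patient near 75% can be put in the wrong class in either direction. If hold days are due, the weights do no harm.

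The expected effect is small. An illustrative simulation assumed that 60% of patients have a 7- to 14-day hold in Course 1, with one to six courses and mean adherence of 75 to 90%. About 1 to 3.5% of patients changed class, which is 0.01 × 25 = 0.25 to 0.035 × 25 = 0.9 patients. At an assumed mean adherence of 95% the rate was about 0.5%. The documents give none of the adherence figures, and the result depends on them. Zero or one patient is the likely number, though each patient is 1/25 = 4 percentage points of the reported proportion. No primary or secondary endpoint changes.

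**What to change.** In SAP 7.3, replace the day-weighted average with:

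overall compliance (%) = 100 × (sum of doses taken) / (sum of doses due), over all scored intervals.

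Add one sentence stating whether days on a treatment hold count as doses due. Replace the illustration with one that includes a hold and gives its numerical result.

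The pooled formula equals day weighting whenever doses due are proportional to days, so it is safe under either definition. It also removes the mismatch between the illustration's weights and its calendar-span denominator, because it uses no dates as weights.

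The cost is a small change of SAP wording and one line of code. It needs no new data.
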